### Visit 03: End of Therapy Visit (Day 5-10+2)

The EOT visit will occur within 2 days of the completion of oral therapy. At the EOT visit, subjects will be assessed for clinical and microbiological outcome and safety. If the subject experiences a clinical/microbiologic failure, the subject will be referred to the primary medical provider for further management. An EOT visit will occur even for subjects who stopped study drug before EOT.

The following procedures will be completed according to Appendix A.

- Review of concomitant medications
- Assessment of study drug compliance (pill/sachet count)
- Review of memory aid and assessment of solicited adverse events
- Assessment of cUTI signs and symptoms and investigator's assessment of improvement
- Limited physical exam (abdominal, flank, and suprapubic palpation, and examination of any other body site as indicated by subject symptomatology) with vital signs (blood pressure, heart rate, respiration rate, temperature)
- Collection of blood sample for blood culture if subject is febrile and/or at investigator's discretion
- Collection of urine specimen for culture
- Collection of AEs and SAEs grade 2 and above, and AESI of any grade.
- Collection of blood (t=24 hours) and urine (t=4-24 hours) if subject consented for Future Use Samples and Data (Section 7.8)

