## 7.6. Early Termination Visit (if needed)

If a subject/subject's LAR withdraws (but still consents for the visit) or is withdrawn from the trial, every effort should be made to complete an early termination visit. If the subject presents to the Early Termination visit with symptoms concerning for active illness in need of medical attention, the study team will refer the subject to seek care and to follow up with their primary care provider. At the early termination visit, all assessments that would have been completed at the EOT visit should be made, including:

- Review of concomitant medications
- Assessment of study drug compliance if visit occurs before the EOT visit and collection of dispensed antibiotics.
- Review of memory aid and assessment of solicited adverse events if visit occurs before the EOT visit
- Assessment of cUTI signs and symptoms and investigator's assessment of improvement
- Limited physical exam (abdominal, flank, and suprapubic palpation, and examination of any other body site as indicated by subject symptomatology) with vital signs (blood pressure, heart rate, respiration rate, temperature)
- Collection of blood sample for blood culture if subject is febrile and/or at investigator's discretion
- Collection of urine specimen for culture
- Collection of AEs grade 2 and above or AESI of any grade if visit occurs before EOT, or SAEs if visit occurs before TOC

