5. SAMPLE SIZE CONSIDERATIONS

This is a Phase IV multicenter, open-label, randomized pragmatic superiority clinical trial comparing two strategies for step-down oral therapy for cUTI. The basic null hypothesis of this trial is:

H0: The probability of success (clinical cure and microbiological cure) at TOC is not conditional on the treatment strategy.

This hypothesis testing question will result in one of three statements regarding the results of this trial:

1. Strategy 1 is superior to Strategy 2.
2. Strategy 2 is superior to Strategy 1.
3. Evidence from the trial is insufficient to conclude that either strategy is superior.

The primary analysis will use the micro-ITT population, defined as all randomized subjects who have a positive baseline bacterial culture of urine. Subjects will not be excluded from this population based upon events that occurred post-randomization (e.g., loss to follow-up). An assumption of 92% micro-ITT eligibility is made for the sample size calculations. If 634 subjects are enrolled with 1:1 allocation, 291 subjects per arm would be expected to qualify for the micro-ITT population. Assuming a 10% difference in treatment success at TOC, with 80% success for one strategy and 70% success for the other strategy, there will be 80% power to reject the null hypothesis using a two sided ztest (without continuity correction), with a Type I error rate of 5%. These calculations assume an interim analysis after 40% of subjects have completed the study, with Type I error controlled using Lan DeMets with an O'Brien Fleming spending function. The specific success rates of 70% and 80% are based on a 10% clinically significant difference an approximate rate of success consistent with example calculations in the FDA guidance for cUTI studies. Sample size calculations were computed using PASS 2008 software. The calculations do not adjust for dropout, because analysis methods will include subjects that have dropped out early, assuming they meet micro-ITT criteria (Section 6.3.1).

If true success rates are instead 65% and 75%, there will be 75% power to conclude a difference in the strategies. If true success rates are 80% and 90%, there will be 92% power to conclude a difference.

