8.4. Imputation of Missing Data

8.4.1. Multiple Imputation of Missing Values of Treatment Success at TOC and EOT

Primary and secondary analyses depend on multiple imputation of treatment success at TOC and EOT, respectively. First, a table showing the number and percentage of missing data for each outcome at EOT and TOC will be presented in [Table 18](#). In order to use the MI model to adjust for bias caused by missing data, we assume that data is missing at random (MAR). To test this assumption, we will fit a logistic model for missing data indicator D (1 if missing, 0 if non-missing) adjusting for covariates of the MI model listed below. Parameter estimates, 95% confidence intervals, and p-values from this model will be provided in

Table 19 at TOC and at EOT. If some of these covariates have a significant relationship with the missing data indicator ($p\text{-value} \leq 0.05$), then the MAR assumption is more likely than MCAR.

In case of missing treatment success at TOC or EOT, multiple imputations of missing treatment success at TOC or EOT will be performed independently, and each subject will have their missing endpoints imputed independently of other subjects' imputations using a subject-specific imputation model. The pseudocode shown below details how missing data for treatment success at TOC (or EOT) will be imputed using m multiply imputed datasets from linear models. The following covariates will be considered for the MI model: treatment strategy, site indicators, age, sex, pyelonephritis status, and number of bacterial species. The number of imputed, m , datasets will be chosen based on the average percent of missing data. Default value will be $m=20$ since sample size calculation assumed a 20% drop-out rate. Similar models will be fit for clinical cure and microbiological success.

As a first step to multiple imputation, an ordered list of variables to include in the subject-specific imputation model will be constructed. Ordering is specified so that exact imputation results from final data are prespecified may be replicated in SAS (using seeds described below). The complete ordered list of variables for the imputation models for treatment success, clinical cure, and microbiological success at TOC and EOT is below:

- Treatment Strategy (Strategy 2 is the reference)
- Indicator of subject enrolled at the site with the second most number of subjects enrolled (binary indicator)

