- Indicator of subject enrolled at the site with the third most number of subjects enrolled (binary indicator)
- Indicator of subject enrolled at the site with the fourth most number of subjects enrolled (binary indicator)
- Indicator of subject enrolled at the site with the least number of subjects enrolled (binary indicator)
 - Note: the site with the most number of subjects enrolled is reference for site. Language is written to allow for an arbitrary number of sites. In the event of a number of ties for the number of subjects enrolled, tied sites will be ordered in ascending alphanumeric order in the list of model variables.
- Age at enrollment
- Sex (Male is the reference)
- Indicator for pyelonephritis (No is the reference)
- Number of species detected in the urine at baseline (1 is the reference)

The actual list of MI model variables for each subject-specific imputation model will follow the ordering above but omit variables with missing values. The below pseudo-code / SAS code outlines the creation of 20 multiple imputation datasets. Note that the seeds used in the actual analysis must follow the specification given in the pseudo-code and subjects must be processed in the order described in the pseudo-code. Clinical cure and microbiological success will simultaneously be imputed with composite cure at each respective time point. The pseudo-code is in terms of TOC endpoints, but the general logic is also applicable to the EOT.

*Outcome variables: trtsuccess clincure microsuccess

DEFINE i=index variable for subjects having treatment success imputed.

Subjects requiring imputation are sorted in ascending order
by PATID.

DEFINE N=number of subjects requiring imputation

DEFINE g&i=analysis dataset containing predictors and treatment success for
CC-TOC subjects as well as subject i (only one subject not in
CC-TOC included). Note that CC-TOC subjects that are missing a value
for one or more variables in the subject-specific imputation model are excluded.

DEFINE imp_g&i = g&i, with 20 imputed values for the missing treatment success
added by PROC MI

DEFINE &&modelVars_&i = list of observed variables in subject i (site1, site2, site3, site4, age, sex,
treatment strategy, pyelonephritis, Nbacterias), to be used for imputation of treatment success, clinical cure,
and microbiological cure.

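### The TOC imputation model in SAP 8.4.1 leaves out the observed EOT outcome, so TOC cure rates are biased upward if EOT failures miss TOC more often, and the treatment difference is biased in a direction that cannot be known in advance

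*SAP*

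**What the plan says.** SAP 8.4.1 says of the two visits that "multiple imputations of missing treatment success at TOC or EOT will be performed independently". Its ordered list of predictors holds strategy, site indicators, age, sex, pyelonephritis and number of species at baseline. The code regresses each TOC outcome on that list and nothing else. Under SAP 6.3 and 8.4.1, micro-ITT subjects outside the complete-case TOC population are imputed. They include early terminations before TOC and subjects with a missing or contaminated TOC culture.

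The model assumes missing at random. The planned check (Table 19) is a logistic regression of missingness on the same baseline covariates.

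The list is adapted subject by subject: "The actual list of MI model variables for each subject-specific imputation model will follow the ordering above but omit variables with missing values".

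The EOT information exists. Protocol 7.3 (Visit 03) collects symptoms and a urine culture at EOT, including from subjects who stopped study drug early. Protocol 7.6 adds: "At the early termination visit, all assessments that would have been completed at the EOT visit should be made". On failure found at EOT, Visit 03 says: "If the subject experiences a clinical/microbiologic failure, the subject will be referred to the primary medical provider for further management".

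**The concern.** Take two subjects with the same strategy and baseline profile, both missing at TOC. One was free of symptoms with a clear culture at EOT; the other was symptomatic with a positive culture. The SAP draws their TOC results from the same distribution, although what is known about them differs sharply.

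This does harm if leaving before TOC depends on the EOT result. Referral of EOT failures to another provider makes such dependence plausible. Missing at random would then fail given the SAP's covariates, while it might hold, at least approximately, once EOT status is included. The Table 19 check cannot reveal the problem because EOT status is not among its covariates.

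At stake are the primary estimate and the arm-level cure rates in Table 20, which is intended for the primary manuscript.

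**Working it through.** **The plan's own figure.** SAP 5 states: "Assuming a 10% difference in treatment success at TOC, with 80% success for one strategy and 70% success for the other strategy"; and "If 634 subjects are enrolled with 1:1 allocation, 291 subjects per arm would be expected to qualify for the micro-ITT population". For a two-sided 5% z-test without continuity correction, power = Φ[(0.10 − 1.96·SE₀)/SE₁].

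- At 291 per arm: SE₀ = √(2·0.75·0.25/291) = 0.0359, SE₁ = √((0.16 + 0.21)/291) = 0.0357. Power = Φ(0.83) = 79.7%, against 80% stated. Allowing for the planned 40% look gives 79.4% to 80.0%.
- At 24 per arm (48 subjects, assumed evenly split): SE₀ = 0.125, SE₁ = 0.124. Power = Φ(−1.17) = 12.1%, against 12% stated.

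The design figures reproduce. They take no account of informative loss before TOC.

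**Closed form for the bias.** Let e be EOT success in an arm, s and f the TOC success rates after EOT success and after EOT failure, and a and q the shares of EOT successes and EOT failures missing at TOC. Suppose the baseline covariates say nothing about EOT status. Then:

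- True TOC rate = e·s + (1−e)·f.
- Expected rate under the SAP model = [e(1−a)s + (1−e)(1−q)f] / [e(1−a) + (1−e)(1−q)], the observed-case rate of the arm.

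None of these inputs is in the documents. Assumed: e = 0.85 (arm A) and 0.75 (arm B), s = 0.90, f = 0.20, a = 0.10.

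True rates: A = 0.765 + 0.030 = 79.5%; B = 0.675 + 0.050 = 72.5%; difference 7.0 points.

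| EOT failures missing (A / B) | Expected A | Expected B | Difference |
|---|---|---|---|
| 50% / 50% | 0.7035/0.84 = 83.75% | 0.6325/0.80 = 79.1% | 4.7 |
| 50% / 25% | 83.75% | 0.645/0.8625 = 74.8% | 9.0 |
| 25% / 50% | 0.711/0.8775 = 81.0% | 79.1% | 2.0 |

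In the first row total missingness is 16% and 20%. With the same pattern in both arms, the difference is 5.9 at 15% of successes and 35% of failures missing, and 3.0 at 5% and 70%. It is unbiased when missingness does not depend on EOT status. Both cure rates are too high in every row; the difference moves either way.

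**Simulation under a second set of assumptions.** Normal-regression imputation without rounding, 20 imputations, 600 runs; s = 0.95, f = 0.20, 5% of EOT successes missing; predictors strategy, pyelonephritis and age, with or without EOT outcome. Shares lost refer to EOT failures.

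| Per arm | True rates | Lost | Difference without EOT (rejection) | Difference with EOT (rejection) |
|---|---|---|---|---|
| 291 | 80/70 | 50%/50% | 6.9 (52%) | 10.0 (79%) |
| 291 | 80/70 | 70%/30% | 14.6 (99%) | 10.0 (80%) |
| 291 | 80/70 | 30%/70% | −1.6 (10%) | 9.9 (79%) |
| 291 | 75/75 | 70%/30% | 8.3 (70%) | 0.1 (6%) |
| 24 | 80/70 | 50%/50% | 7.5 (8.5%) | 11.0 (13.0%) |

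In the first row the cure rates are 86.3% and 79.4% without EOT, and 80.0% and 70.0% with it. The 24-per-arm differences carry a simulation error of about 0.5 points (0.130/√600 = 0.005).

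**Precision.** Under the closed-form assumptions with 50%/50% loss, a separate simulation at 24 per arm gave a standard deviation of the difference of 0.124 for a strategy-only model and 0.130 with EOT added. The expected number of EOT failures observed at TOC is 24·0.15·0.5 + 24·0.25·0.5 = 1.8 + 3.0 = 4.8.

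**The case against.** A reader might infer that EOT failures leave the trial. The documents do not say so. Referral is for further management, and Protocol 7.5 uses the same sentence for failures found at the TOC visit itself. Failure at EOT is not a listed reason for withdrawal. Subjects who stop study drug are to stay in the study and be assessed for success (Protocol 5.3.3, SAP 4.3.3). Only bacteremia, and failures for whom no oral adjustment is possible, are described as followed for safety. This stands: the dependence is plausible but not prescribed, and its frequency is unknown.

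A reader might also infer that the bias always shrinks the difference. That needs similar loss of EOT failures in both arms. The trial is open-label, so loss may differ by arm, and the tables above show widening, reversal and a false difference.

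Some of these subjects may not be missing at all. SAP 3.3 gives treatment failure no time point, and parenteral antibiotics after randomization rule out clinical cure. This stands too, and it determines the order of the fix.

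The sizes rest on assumptions, and recovery of the true value with EOT in the model is built into the simulated data, where missingness depends only on arm and EOT result. The simulations also used fewer covariates than the SAP's list, so the precision cost is indicative.

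Finally, Tables 24 and 25 vary imputed success from 0% to 100% separately by arm, and SAP 5 warns against superiority conclusions at 12% power. The bias in the equal-loss case, 7.0 − 4.7 = 2.3 points, is about 0.19 of the 12.4-point standard deviation. These facts limit the consequences but leave the primary estimate unrepaired, because the grid treats all missing subjects in an arm alike, whatever their EOT result.

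**Conclusion.** The concern holds in this form: the primary TOC imputation discards an observed, strong predictor. If EOT failures miss TOC more often than EOT successes, the cure rate is biased upward in each arm where that happens. The bias in the difference depends on which arm loses more EOT failures. Under the closed-form assumptions a true 7.0 points becomes 4.7, 9.0 or 2.0. With loss unrelated to EOT status there is no bias.

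The documents support neither a rule that EOT failures leave nor a general pull toward zero. With 48 subjects the practical effect is mainly on the reported cure rates and interval, not on a test that already has about 12% power. I would class this as a cheap improvement.

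**What to change.** 1. Before imputing, score as TOC failures those subjects whose outcome the endpoint definition already settles, for example parenteral antibiotic use after randomization. Do not extend this to every EOT failure missing at TOC: if some recover under the definition, that is biased too (simulated difference 11.4 against a true 10.0 at 291 per arm, 50%/50% loss, 20% recovery).
2. Add EOT treatment success to the ordered list for TOC treatment success, EOT clinical cure for TOC clinical cure, and EOT microbiological success for TOC microbiological success. Where there was no EOT visit, use the early-termination assessment.
3. Remove the statement that imputation at the two visits is independent.

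The data are already collected, and the subject-specific rule already drops a predictor that the imputed subject lacks. The change still has costs. It adds one parameter per model at 48 subjects. SAP 8.4.1 excludes complete-case TOC subjects with a missing predictor from any model that contains it, so those without EOT data drop out of the new models. The EOT coefficient will be imprecise, and it cannot be estimated if no EOT failure is observed at TOC. The SAP should say what is done in that event. Tables 24 and 25 stay as sensitivity analyses.

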3.3. Study Definitions and Derived Variables

Clinical cure is defined as:

- Resolution of UTI symptoms from presentation (fever, hypothermia, chills or rigors or warmth, flank pain, flank tenderness, suprapubic pain, pelvic pain, suprapubic tenderness, nausea, vomiting, pain on urination, urinary frequency, urinary urgency)

AND

- No new UTI symptoms

AND

- Avoidance of parenteral antibiotic therapy, in or out of hospital, at any time after randomization **OR** oral antibiotic therapy different from per protocol

A subject will be considered a clinical failure if at least one of the above conditions is not met.

Microbiological success (Microbiologic cure) is defined as:

- Reduction of the pathogen found at presentation to $<10^4$ CFU/mL for non-catheter specimens or $<10^3$ for catheter specimens on urine culture.

Treatment success (composite cure) is defined as:

- Clinical cure and microbiological success.
- Treatment Success will be referred to as Composite Cure in manuscript TFLs.

Treatment Failure is defined as:

- A subject will be considered a treatment failure if the subject experiences clinical/microbiologic failure **OR** if the subject develops bacteremia with a uropathogen after randomization.

Adjustment-free treatment success is defined as:

- Treatment success without therapy adjustments.

Relapse infection is defined as:

- Recurrence of UTI symptoms between EOT and TOC.

End of Therapy (EOT) Visit is also referred to as Visit 3 in the protocol and will occur within 2 days of the completion of oral therapy. The window for this visit is Day 5-10 +2 days.

Test of Cure (TOC) Visit is the final visit for this study (Visit 4) and will be scheduled within the window of Day 21 + 7 days after randomization.

Day 1: is defined as the day of first dose for subjects who were treated with study product. For subjects not treated with study product, Day 1 will be defined as the day of randomization.

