6.3. Analysis Populations

The primary analysis will be performed using the micro-ITT population. Other analyses, as specified below, may use the complete cases (CC) at Test of Cure or End of Therapy (CC-TOC or CC-EOT) populations. Analyses of the micro-ITT population will include imputation for missing data (Section 8.4), while analyses of the CC populations will not contain missing data by design. Analysis of clinical cure will use the ITT analysis population and will include imputation for missing data. Analysis of clinical cure will be repeated to use all subjects in ITT with complete data. Analysis of unsolicited events will use the Fosfomycin safety analysis population while analysis of solicited events will use both the Safety and Fosfomycin Safety populations.

Reasons for exclusion from each analysis population are summarized in [Table 7](#) and shown by subject in [Listing 4](#). Excluded subjects might satisfy multiple criteria justifying their exclusion but will have only the first exclusion criteria met for a given population indicated in [Table 7](#) and [Listing 4](#). The reason indicated will be determined by the following rules in order.

ITT Analysis Exclusion Reasons:

- Subject not randomized

Micro-ITT Analysis Exclusion Reasons:

- Subject does not have a baseline culture from a urine sample taken prior to treatment with study drug
- Baseline culture is not positive for a uropathogen or is contaminated

CC-TOC Analysis Exclusion Reasons:

- Subject not in micro-ITT population
- Subject not treated with at least one dose of study product
- Early termination before TOC
- Missing urine culture or had a urine culture that was contaminated at TOC

CC-EOT Analysis Exclusion Reasons:

- Subject not in micro-ITT population

-
- Subject not treated with at least one dose of study product
 - Early termination before EOT
 - Missing urine culture or had a urine culture that was contaminated at EOT

Safety Analysis Exclusion Reasons:

- Subject not treated with at least one dose of study product

Fosfomycin Safety Analysis Exclusion Reasons:

- Subject not treated with at least two doses of Fosfomycin

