Step 1: Imputation model: This model will generate 20 datasets with each dataset containing original complete data along with imputed values for subjects with missing endpoint.

```
%do i=1 %to &N;
```

```
PROC MI data= g&i out= imp_g&i seed= 22131&i NIMPUTE=20 noprint;
  Var &&modelVars_&i trtsuccess_TOC clincure_TOC microsuccess_TOC;
  monotone regression(trtsuccess_TOC = &&modelVars_&i);
  monotone regression(clincure_TOC = &&modelVars_&i);
  monotone regression(microsuccess_TOC = &&modelVars_&i);
```

```
run;
```

```
%end;
```

imp_g&i will be subset to contain only rows for the subjects with imputed treatment success, clinical cure,
and microbiological success and merged together and with CC-TOC data to create the twenty complete
multiply imputed datasets

Step 2: Analysis model: This model will fit regression models to the 20 complete datasets to obtain parameter estimates for treatment success, clinical cure, microbiological success.

```
proc reg data= imp_g outest= out_trts covout noprint;
```

```
model trtsuccess= trt /clb alpha=0.05;
```

```
by _imputation_;
```

```
run;
```

```
proc reg data= impdata outest= out_clinc covout noprint;
model clincure= trt /clb alpha=0.05;
by _imputation_;
run;

proc reg data= impdata outest= out_micros covout noprint;
model microsucceed= trt/clb alpha=0.05;
by _imputation_;
run;
```

Step 3: Combine estimates from models in step 2 to obtain overall estimates summarized over 20 imputed datasets;

```
proc mianalyze data= out_trts alpha = 0.05;
modeleffects trt;
ods output ParameterEstimates=parms_trts;
run;

proc mianalyze data= out_clinc alpha = 0.05;
modeleffects trt;
ods output ParameterEstimates=parms_clinc;
run;

proc mianalyze data= out_micros alpha = 0.05;
modeleffects trt;
ods output ParameterEstimates=parms_micros;
run;
```

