Clinical cure is defined as: 1) Resolution of UTI symptoms from presentation and 2) No new UTI symptoms and 3) Avoidance of parenteral antibiotic therapy, in or out of hospital, at any time after randomization OR oral antibiotic therapy different from per protocol.

Microbiological cure is defined as a reduction of the pathogen found at presentation to <104 CFU/mL for non-catheter specimens or < 103 for catheter specimens on urine culture.

Treatment success (composite cure) is defined as clinical cure and microbiological success.

Table 21: Comparison of Composite Cure, Clinical Cure and Microbiological Cure Rates at TOC and EOT by Treatment Group, Complete Case at EOT and TOC Populations*

[Implementation note: This table will be provided to the PI for the paper manuscript as Table 2B.]

| Endpoint | Strategy 1 | | | Strategy 2 | | | Difference (95% CI) ^a | P-value ^c |
|--|----------------|---|---|----------------|---|---|----------------------------------|----------------------|
| | N ^b | n | % | N ^b | n | % | | |
| Complete Case at Test of Cure | | | | | | | | |
| Composite Cure | x | x | x | x | x | x | x (x.x, x.x) | x.xxx |
| Clinical Cure | x | x | x | x | x | x | x (x.x, x.x) | x.xxx |
| Microbiological Success | x | x | x | x | x | x | x (x.x, x.x) | x.xxx |
| Complete Case at End of Therapy | | | | | | | | |
| Composite Cure | x | x | x | x | x | x | x (x.x, x.x) | x.xxx |
| Clinical Cure | x | x | x | x | x | x | x (x.x, x.x) | x.xxx |
| Microbiological Success | x | x | x | x | x | x | x (x.x, x.x) | x.xxx |

^a 95% Wald CI without continuity correction will be provided.^b N = Number of subjects in CC-TOC (or CC-EOT). Note that this varies by endpoint depending on whether the subjects are missing composite cure, clinical cure or microbiological cure at TOC (or EOT). n = number of subjects with cure.^c P-value from the linear regression model using the Wald method**Clinical cure** is defined as: 1) Resolution of UTI symptoms from presentation and 2) No new UTI symptoms and 3) Avoidance of parenteral antibiotic therapy, in or out of hospital, at any time after randomization OR oral antibiotic therapy different from per protocol.**Microbiological success** is defined as a reduction of the pathogen found at presentation to <104 CFU/mL for non-catheter specimens or < 103 for catheter specimens on urine culture.**Treatment success (composite cure)** is defined as a combination of clinical cure and microbiological success.

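### The imputation of composite cure ignores a clinical result observed at the same visit, so cured subjects without a culture are imputed too low, failed ones too high, and the monotone code does not fit either

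*SAP*

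**What the plan says.** SAP 3.3 defines treatment success (composite cure) as "Clinical cure and microbiological success", and adds: "A subject will be considered a treatment failure if the subject experiences clinical/microbiologic failure". An observed failure on either component therefore settles composite as 0.

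SAP 8.4.1 lists the predictors: "The following covariates will be considered for the MI model: treatment strategy, site indicators, age, sex, pyelonephritis status, and number of bacterial species". All of them describe the subject at baseline. On the three outcomes it says: "Clinical cure and microbiological success will simultaneously be imputed with composite cure at each respective time point". In the Step 1 code the variable list is "Var &&modelVars_&i trtsuccess_TOC clincure_TOC microsuccess_TOC", and composite is imputed by "monotone regression(trtsuccess_TOC = &&modelVars_&i". The lines for clinical cure and microbiological success use the same baseline list. No line uses one outcome to predict another.

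SAP 6.3 gives this as a reason for leaving the complete-case population at TOC: "Missing urine culture or had a urine culture that was contaminated at TOC". The same applies at EOT. Subjects outside that population are the ones imputed in 8.4.1. The plan expects some of them to have one component known: Table 18 counts missing values by endpoint, and the Table 21 note on N says: "Note that this varies by endpoint depending on whether the subjects are missing composite cure, clinical cure or microbiological cure at TOC (or EOT".

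**The concern.** Suppose a subject attends TOC, is clinically cured and has no usable culture. By the SAP's own definition, composite for this subject equals microbiological success, so the quantity to impute is the chance of microbiological success given clinical cure. The code instead draws from a model fitted to everyone with known composite, clinical failures included. That mean is lower whenever clinical cure is below 100%.

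The mirror case is a clinical failure without a culture. Composite is known to be 0, yet 6.3 can be read as sending the subject to imputation, where the same model gives a value near the overall rate.

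At stake are the primary estimate and Table 20. Information collected at the visit is set aside. Because the three outcomes are drawn separately, an imputed composite can exceed its own components. The prespecified code also assumes a missing-data pattern that these subjects do not have.

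**Working it through.** **Inputs.** From SAP section 5: composite success 80% vs 70%, two-sided 5% test, 291 per arm planned, 48 micro-ITT subjects achieved (taken as 24 per arm), stated power 80% and 12%. From SAP 8.4.1: 20% drop-out as the planning figure. Assumed, because the documents do not give them: clinical cure 80–95%, and 20% of cultures missing (30% vs 10% for an unequal case).

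**1. The plan's own figures.** Power = Φ((0.10 − 1.96·√(2·0.75·0.25/n)) / √((0.16 + 0.21)/n)).
- n = 24: (0.10 − 0.245)/0.1242 = −1.168, so power is 0.121 (stated 12%).
- n = 291: (0.10 − 0.0704)/0.0357 = 0.831, so power is 0.797 (stated 80%).

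The composite rates of 70% and 80% are therefore used below.

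**2. Cured subject, no culture.** The correct mean is P(composite)/P(clinical cure). The model gives about P(composite).

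| Composite | Clinical cure (assumed) | Correct mean | Shortfall |
|---|---|---|---|
| 0.70 | 0.80 | 0.875 | 0.175 |
| 0.70 | 0.85 | 0.824 | 0.124 |
| 0.70 | 0.90 | 0.778 | 0.078 |
| 0.70 | 0.95 | 0.737 | 0.037 |
| 0.80 | 0.85 | 0.941 | 0.141 |
| 0.80 | 0.90 | 0.889 | 0.089 |
| 0.80 | 0.95 | 0.842 | 0.042 |

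Composite 0.80 with clinical cure 0.80 is left out because it would need every cured subject to be a microbiological success.

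**3. Failed subject, no culture.** The correct value is 0. If imputed, the subject receives about 0.7–0.8.

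**4. Arm level, 20% of cultures missing independently of outcome.**
- *Case A, both groups imputed.* The two errors offset. A simulation of the SAP's method (normal linear regression, no rounding, m = 20, baseline predictors, 24 per arm, clinical cure 90%/85%) gives arm rates of 0.803/0.699 against true values of 0.80/0.70.
- *Case B, clinical failures counted as observed failures.* With q the share of cultures missing, the expected arm rate is (1 − q)·P(composite) / (1 − q·P(clinical cure)).
  - 0.70 with 0.80: 0.56/0.84 = 0.667, bias −0.033
  - 0.70 with 0.85: 0.56/0.83 = 0.675, bias −0.025
  - 0.80 with 0.90: 0.64/0.82 = 0.780, bias −0.020
  - 0.80 with 0.95: 0.64/0.81 = 0.790, bias −0.010

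  The simulated rates for 80%/70% are 0.780/0.677, so with equal missingness the difference (0.104) hardly moves.
- *Case B, unequal missingness.* With 30% missing in the 80% arm and 10% in the 70% arm: 0.56/0.73 − 0.63/0.915 = 0.767 − 0.689 = 0.079, against a true 0.10. With the shares swapped: 0.72/0.91 − 0.49/0.745 = 0.791 − 0.658 = 0.133.

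**5. Missingness that depends on the clinical result, both groups imputed.** Take clinical cure 85% and microbiological success given cure 88%, so composite is 0.85·0.88 = 0.748.
- 25% of cured and 5% of failed subjects without a culture: 0.75·0.748/(1 − 0.2125 − 0.0075) = 0.561/0.78 = 0.719, about 3 points low.
- The shares reversed: 0.95·0.748/(1 − 0.0425 − 0.0375) = 0.7106/0.92 = 0.772, about 2 points high.

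**6. Monotone pattern.** In the order composite, clinical, microbiological, a subject with only the clinical result is missing–observed–missing. An earlier variable is missing while a later one is observed, so the pattern is not monotone. With clinical cure listed first it becomes observed–missing–missing, which is.

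**7. Scale.** The 95% CI half-width at 24 per arm is 1.96·√(0.16/24 + 0.21/24) = 0.243.

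**The case against.** A reader might infer that the cure rate is biased down in whichever arm has more missing cultures. The documents do not support that without conditions. If 6.3 sends every subject without a culture to imputation, the clinical failures among them are imputed too high and the cured too low, and under missingness unrelated to clinical result these cancel (case A). Downward bias needs either failures already counted under 3.3 or missing cultures concentrated among cured subjects. The SAP does not settle the first. The second is possible, because the protocol (8.2.1 and Appendix A, note g) asks for a culture whenever a subject fails treatment, but it is not established. The planned check of the missingness assumption in Table 19 could not show it, since that model uses the same baseline covariates.

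Other points against have some force. Table 21 repeats the analysis without imputation, and Table 24 varies imputed success from 0% to 100% in each arm, so the error is bounded. SAP section 5 warns against superiority conclusions at 12% power. SAP 8.1.1 openly accepts implausible imputed values. The code is offered as an outline, and if the observed clinical result were blanked in the subject's dataset it would fit.

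What remains is that the sensitivity tables bound the problem without correcting the primary estimate. Blanking would discard an observed outcome from the clinical cure row as well. The SAP states no rule either way, although it fixes the variable order so that results can be replicated exactly.

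**Conclusion.** The point holds per subject and for the code. A cured subject without a usable culture is imputed about 4 to 17 points too low, given composite 70–80% and an assumed clinical cure of 80–95%. A failed subject without a culture would be imputed at about 0.7–0.8 instead of 0 if 6.3 is applied as written. The variable order is not monotone for any subject with clinical cure observed and composite missing.

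The arm-level effect is conditional: near zero in case A, about 1 to 3 points downward in case B with about 20% of cultures missing, and in either direction when missingness depends on clinical result. The difference between arms moves mainly when missingness differs by arm. The number of affected subjects is not given, and subjects with all three outcomes missing fit the code as it stands. How the software would treat a non-monotone pattern is not in the documents and is not relied on. Against the CI half-width at the achieved size the effect is small, but the change is cheap and makes Table 20 internally consistent, so it should be made.

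**What to change.** Amend 8.4.1 for both TOC and EOT, applying both parts together:

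1. If either component is observed as a failure, set composite to 0 without imputation. State in 6.3 that such a subject does not have missing composite.
2. If clinical cure is observed as cured and the culture is missing or contaminated, impute microbiological success from clinically cured complete cases and set composite equal to it. Treat an observed culture success with a missing clinical result in the mirror way.

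Keep the baseline-only model when both components are missing, with donors who have both components observed.

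In the code, list the observed component before the missing ones in the VAR statement and use it as a predictor (it is constant, and drops out, where the donors are restricted to its observed value). In these cases derive composite from the components instead of drawing it separately.

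Neither part is safe alone. With clinical cure 85%, microbiological success given cure 88%, and missingness unrelated to clinical result, the missing-culture group has a true composite rate of 0.748. Part 1 alone imputes it at 0.85·0.748 = 0.636. Part 2 alone imputes it at 0.85·0.88 + 0.15·0.748 = 0.860. With both parts applied in the simulation at 24 per arm (20% of cultures missing), the mean imputed value for a cured subject without a culture rises from 0.73–0.75 to 0.86, and the arm rates are 0.797/0.701 against 0.80/0.70.

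The cost is a few lines of SAP text and code before database lock. No new data are needed.
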